months. V_A and D_L were not associated with GA, mechanical ventilation or oxygen therapy suggesting that in the absence of extreme prematurity and BPD, prematurity itself does not impair lung parenchymal development. However, further analysis of the preterm infants demonstrated that both V_A and D_L were significantly higher (by about 16%) for infants who received any CPAP in the NICU compared to those who had not received any CPAP (Table 1). This was not a controlled trial of CPAP, but our findings suggest that mechanical stretch from CPAP in preterm infants may produce larger, more functional lungs.

Table 1. V_A and D_L in Healthy Preterm Infants According to CPAP Treatment

Lung Function Measures	No CPAP (n=29)	CPAP (n=19)	P value	% difference
V _A (mL)	606.8 ± 171.5	694.6± 205.2	0.046	16%
D _L (mL/min/mmHg)	3.86 ± 0.97	4.49± 1.42	0.007	16%

Values are Mean ± SD; p values adjusted for length and gender

b3c. Pilot Study: The Effect of eCPAP on FRC through NICU discharge, a RCT

We recently published a pilot study randomizing stable preterm infants \leq 32 weeks of gestation at birth and requiring \geq 24 hours of CPAP for respiratory distress to 2 extra weeks of CPAP (eCPAP) versus CPAP discontinuation when CPAP stability criteria were met¹⁶. CPAP stability criteria included: on CPAP of 4-5 cm H₂O; on room air; respiratory rate \leq 70 breaths/minute, retraction score \leq 1; < 3 self resolving apneas (< 20 seconds) and/or bradycardia (< 100 bpm) and/or desaturations (pulse oximeter oxygen saturation, SpO2 <86%) in 1 hour for past 6 hours; average SpO2 >86% for 90% of the time over the past 24 hours, not being treated for a PDA or sepsis, and tolerating time off CPAP during routine care (up to 15 minutes).

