- We anticipate screening 300 infants to recruit the cohort
- Up to 130 infants will be consented once inclusion/exclusion criteria have been verified
- 100 infants will be randomized

b. Inclusion Criteria

- 1) Infants born at >24 to ≤ 32 weeks gestation
- 2) Treated with CPAP for ≥ 24 hours for respiratory distress (either as initial therapy or following extubation)

c. Exclusion Criteria

- 1) Significant congenital heart disease
- 2) Major malformations
- 3) Chromosomal anomalies
- 4) Culture proven sepsis at consent

- 5) Complex maternal medical conditions
- 6) Clinical instability
- 7) Multiple gestations > twins
- 8) <3rd or >97th percentile for weight⁸⁵
- 9) Participating in another neonatal randomized clinical trial with a competing outcome
- **10)** Mother/legal guardian without stable method of communication

Additional criteria that must be met prior to randomization:

- 1) CPAP stability criteria met for at least 12 hours
 - The following CPAP stability criteria 16;86 has to be met for more than 12 hours by 34 weeks of CGA:
 - o CPAP of 5 cmH2O
 - o On room air
 - o Respiratory rate ≤70 bpm without significant retractions
 - <3 self-resolving apneas or bradycardias or desaturations in 1 hour in last 6 hours

 - Average SpO2 >86% for 90% of the last 24 hours
 - Not being treated for a patent ductous or sepsis
 - o Tolerating CPAP "cares"

d. Vulnerable Populations

Neonates will be included in this research. The inclusion of neonates is critical to the research because we have pilot data in preterm infants demonstrating that eCPAP may stimulate lung growth. However, our initial trial did not include follow-up testing after discharge to determine the potential duration of the effect of eCPAP on lung volumes and did not include measurements of lung diffusing capacity. Parent or guardian permission will be obtained before the child will be enrolled in the study, as per IRB guidelines.

e. Setting

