
j. Removal of Patients from Allocated Treatment Arm or from the Study

The investigator or the parents of the preterm infant may discontinue treatment arm allocation or withdraw the infant early from the study at any time for safety or administrative issues. The infant may be withdrawn from the treatment arm per parent request, protocol violation, worsening clinical condition, or investigator decision. Infants who discontinue study arm/treatment allocation will remain in the study for outcome measurements, unless the consent is withdrawn.

6. Study Procedures Involved

a. Clinical Data Collection in NICU

Pertinent maternal and infant data through discharge from the NICU will be collected, including: maternal: age; parity; smoking history; antenatal steroid treatment; etiology of preterm delivery; birth weight and gestational age; surfactant dosing; duration of: oxygen, mechanical ventilation and CPAP (prior to study randomization); respiratory medications; gestational age at full nipple feeds and at discharge.

During the 2-week treatment period detailed data will include daily weights; weekly lengths; calories per day; apneic episodes; oxygenation needs; parental interactions; developmental interactions such as frequency and duration of time spent skin to skin with a parent.

In addition, downloads of continuous oxygen saturation will be done during the two week treatment period with a separate pulse oximeter (will not be used for clinical care so monitor will be covered from caretaker and alarms disabled) with a 2 second averaging time and a 2 second sample rate (Radical; Masimo Corp., Irvine, California) monitors. Intermittent hypoxemia (IH) events will be defined as an oxygen saturation \leq 80% for \geq 20 seconds and \leq 180 seconds as previously described⁷⁸⁻⁸⁰. Episodes of IH and other patterns of oxygen saturation will be compared between the groups.

b. Blood for Epigenetics and Proteomics

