General linear mixed models (GLMMs) will be used to compare the primary outcomes of alveolar volume (V_A) between the eCPAP and dCPAP while adjusting for the design factor gestational age at delivery (28 and 6/7 and 29 and 0/7 weeks) and other baseline variables that are found to be statistically different between the two groups. Since the lung function measures are highly dependent on infant length and sex, we will further adjust for length and sex in the GLMMs. In order to adjust for intra-twin correlations, generalized Estimating Equations (GEEs) with the linear link function will be used to model $V_{A...}$ The GLMMs can be performed using the GEE estimation approach. Intention to treat analysis will be used for all aims as the primary analysis. The intention to treat population is defined as all randomized infants and the analysis uses the assigned randomization group even if infants did not complete the intervention. In addition, a per protocol analysis will be completed for all aims. The per protocol population is defined as all infants who successfully completed the treatment arm to which they were assigned.

b2. Specific Aim 2 (Secondary Outcomes)

Lung diffusion (D_L) and FEF₅₀ will be will be analyzed with the same general approaches described for the primary outcome in SA #1.

b3. Specific Aim 3 (Exploratory Outcomes)

Logistic regression models will be used to compare the incidence of wheeze and the incidence of wheeze and cough between the two groups adjusting for GA at delivery (<29 vs ≥ 29 weeks). Neurodevelopmental scores will be analyzed with the same general approaches described for the primary outcome in Specific Aim 1.

c. Missing Data

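### Duration of CPAP before randomization is collected but not a prespecified covariate for V_A and D_L; it enters the models only if a baseline test finds the arms different

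*Protocol*

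**What the plan says.** **Background evidence.** Protocol section 2, b3b describes 48 preterm infants without BPD, 29 with no CPAP and 19 with some. It states that "V_A and D_L were not associated with GA, mechanical ventilation or oxygen therapy", but that "both V_A and D_L were significantly higher (by about 16%) for infants who received any CPAP in the NICU". Table 1 gives p=0.046 for V_A and p=0.007 for D_L, adjusted for length and gender. The protocol itself notes that the comparison was uncontrolled.

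**Exposure at entry.** Every infant must have been "Treated with CPAP for ≥ 24 hours for respiratory distress" (protocol 5.b). The stability criteria must be met by 34 weeks corrected age (5.c).

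**Data.** The NICU data listed in protocol 6.a include "duration of: oxygen, mechanical ventilation and CPAP (prior to study randomization".

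**Models.** For V_A, protocol 7.b1 adjusts for the two-level gestational-age stratum and for "other baseline variables that are found to be statistically different between the two groups", and adds "we will further adjust for length and sex in the GLMMs". SAP Aim 1 keeps the same structure, including the clause on variables that differ. D_L and FEF50 are to be "analyzed with the same general approaches described for the primary outcome in SA #1". Neither document names prior CPAP as a covariate, and neither gives a threshold for a statistical difference.

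**The concern.** The trial asks whether 14 more days of CPAP enlarge the lung. Infants arrive with anything from 24 hours of CPAP to, at the extreme, about 10 weeks (birth near 24 weeks, randomization near 34). If CPAP duration affects V_A, earlier days should help predict it. If longer CPAP instead marks sicker lungs, it should still predict V_A, with the opposite sign. In either case it is a natural baseline covariate for the primary model.

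The plan leaves its inclusion to a baseline significance test. Such a test measures chance imbalance, not prognostic value. A prognostic variable that is reasonably balanced is left out, its variance stays in the error term, and any imbalance short of significance goes uncorrected. The primary model also becomes dependent on the data.

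**Working it through.** **1. The plan's own figure.** Inputs from protocol 7.a and the SAP power section: mean V_A 642 mL, SD 189, 12% difference, alpha 0.05 (taken as two-sided), 80% power, 34 per group.

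- Difference: 0.12 × 642 = 77.04 mL; 77.04/189 = 0.408 (0.42 is printed).
- Without covariates: n = 2 × (1.96 + 0.8416)² / 0.408² = 95 per group (89 at 0.42). Power at 34 per group is 39%.
- The 34 is reached only if covariates explain about 63–65% of the variance, a figure neither document states. With R2 = 0.63 the residual SD is 189 × √0.37 = 115 mL, and power for 12, 15 and 17% is 78.9, 93.2 and 97.5%, against the printed 80, 92 and 97.

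The planned power already depends on strong covariates. The undocumented R2 is a separate and larger gap.

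**2. Gain from always adjusting.** Let r² be the share of the remaining V_A variance explained by prior CPAP days, beyond stratum, length and sex. The documents do not give r²; it is assumed. Residual SD = 115 × √(1 − r²); power = Φ(77.04 / (SD × √(2/34)) − 1.96).

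| r² | Residual SD (mL) | Fall in SE | Power at 34 per group | n per group for 80% |
|---|---|---|---|---|
| 0 | 115 | 0% | 78.9% | 35 |
| 0.02 | 114 | 1.0% | 79.7% | 35 |
| 0.05 | 112 | 2.5% | 80.9% | 34 |
| 0.10 | 109 | 5.1% | 83.0% | 32 |

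At r² = 0.20 power would be 87.1%. For scale only, the Table 1 p values imply partial R2 of about 0.09 for V_A (t = 2.05: 4.22/(4.22 + 44)) and 0.15 for D_L (t = 2.83: 8.01/(8.01 + 44)), assuming 44 degrees of freedom. Those describe any CPAP versus none, a contrast that does not vary in this trial.

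**3. What the conditional rule recovers.** Simulation with 34 per arm and 20,000 runs, trigger at p<0.05:

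| r² | Never adjust | Conditional rule | Always adjust |
|---|---|---|---|
| 0.05 | 78.2% | 78.2% | 79.5% |
| 0.10 | 77.7% | 77.8% | 81.2% |
| 0.20 | 78.1% | 78.8% | 85.9% |

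The trigger fired in about 5% of runs. Type I error was 4.5–5.2% and mean bias about zero under all three.

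**4. Effect of an imbalance that goes unadjusted.** Assume an SD of 14 days for CPAP duration. Pilot Table 2 gives an SD of birth-to-randomization time of 1.7–2.3 weeks (about 12–16 days), taking the correlation between birth and randomization age as 0 to 0.5.

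- Gap needed for p<0.05 with 50 per arm: 1.984 × 14 × √(2/50) = 5.6 days.
- Illustrative gap below that: 4.2 days, the pilot arms' difference in time from birth to randomization ((32.0 − 28.7) − (32.2 − 29.5) = 0.6 weeks).
- Shift in V_A = (4.2/14) × √r² × residual SD. With 111.7 mL (the residual SD giving 80% power at 34 per group by the t distribution): 0.3 × √0.05 × 111.7 = 7.5 mL; 0.3 × √0.15 × 111.7 = 13 mL. That is 1.2–2.0% of 642 mL.

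**The case against.** Much of the opposing case stands.

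- **The plan has a route to adjustment.** A reader might infer that the models ignore prior CPAP altogether. They do not: a significant imbalance would bring it in. The criticism is of the rule.
- **The cohort evidence is not about duration.** It is an observational any-versus-none contrast in 19 and 29 infants. All trial infants have had CPAP, and no duration relation with V_A or D_L is reported. It makes prior CPAP a sensible candidate and does not show that days are prognostic.
- **Validity is intact.** A reader might infer that chance imbalance biases the primary effect. Randomization makes the estimate unbiased on average, and its standard error already covers chance imbalance.
- **A trial-sized slope is not supported.** A reader might apply the 12% target per 14 days to earlier CPAP days. With an SD of 14 days, that slope would have prior CPAP explain (77.04/111.7)² = 48% of the residual V_A variance. Nothing in the documents supports this.
- **The pilot gap is not a gap in CPAP days.** It is postnatal age, which only caps CPAP duration and can include ventilated time. It arises from birth gestational age (29.5 versus 28.7 weeks), on which this trial stratifies. With 50 per arm and SD 14 days, the SE is 14 × √(2/50) = 2.8 days, so 4.2 days is a 1.5-SE event even before stratification.
- **Overlap with gestational age may leave little to gain.** If age at randomization is independent of birth age, the pilot SDs put the correlation of birth age with postnatal age at about 0.94 in size (1.9/√(1.9² + 0.7²)). A two-level stratum captures only part of this, but r² could still be small.

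None of this favours keeping the significance trigger for this variable.

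**Conclusion.** The point holds as a modest one about precision. Prior CPAP duration is available and is the natural candidate on the protocol's own evidence, yet its inclusion is left to a rule that seldom fires and is blind to prognostic strength. Prespecifying it would add about 1, 2 and 4 power points at 34 per group for r² of 0.02, 0.05 and 0.10, more only if r² is larger, and nothing if it is zero. A 4.2-day imbalance would move V_A by about 7.5–13 mL for r² of 0.05–0.15, against the 77 mL target, and by less to the extent that gestational-age stratification limits it.

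These sizes rest on an assumed r², an assumed SD of 14 days and a back-solved residual SD of 112–115 mL. The same reasoning applies to D_L, which has the same planned n and nearly the same standardized difference (0.12 × 4.1/1.19 = 0.413). The documents do not support a claim of bias or of inflated type I error.

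**What to change.** In protocol 7.b1 and 7.b2 and SAP Aims 1 and 2, name days of CPAP before randomization, as a continuous variable, as a covariate in the V_A and DLCO models alongside the gestational-age stratum, length and sex. State that it is included whatever the observed balance, replacing the significance-triggered rule for this variable. Make the change before treatment allocation is unblinded.

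The cost is one sentence in each place and one degree of freedom. The data are already collected. Overlap with gestational age may shrink the gain, but it complicates only the reading of the covariate coefficients, not that of the treatment effect.

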f. Recruitment and Data Collection Period	26
g. Final Analysis	26
Annondix A	22

Extending CPAP Therapy in Stable Preterm Infants to Increase Lung Growth and Function: A Randomized Controlled Trial

PROTOCOL AMENDMENT HISTORY

Version number, date	Alterations
Version 2.0, 3/9/2020	Clarification of measurement of FRC before randomization, addition of PHSW site

1. Objectives

The objective of this randomized clinical trial is to determine the efficacy of extended continuous positive airway pressure (eCPAP) to improve lung growth and lung function in preterm infants, measured at six months of age. Prematurity occurs in 10% of births and is the most common cause of impaired lung development and increased respiratory morbidity¹. In the early 1970's, CPAP was used to acutely increase lung volumes and improved survival of preterm infants with respiratory distress. The subsequent addition of antenatal steroids, surfactant, and intubation with mechanical ventilation (MV) became the standard of care for several decades². Despite these advances, prematurity still caused impaired lung development³ with decreased airway⁴ and parenchymal function⁵, and increased respiratory morbidity lasting into adulthood. *No current therapies exist to stimulate lung growth, improve lung function, and thus decrease respiratory morbidity after preterm birth.*

Nasal CPAP at birth is now standard care to stabilize and maintain functional residual capacity (FRC), to avoid atelectrauma, volutrauma, intubation, and to reduce bronchopulmonary dysplasia (BPD)^{2;6-9}. Although early CPAP use has been well studied, there are few studies defining the optimal time to discontinue CPAP in preterm infants¹⁰. Early CPAP use may benefit the preterm lung by minimizing injury; but, clinical and animal data indicate that mechanical stretch of the lung with CPAP may provide an important benefit of stimulating lung growth. Congenital diaphragmatic hernias (CDH) compress the lung in-utero causing lung hypoplasia^{11;12}, and increasing intra-tracheal pressure in-utero stimulates lung growth in CDH models¹³. We found 1-week of

CPAP increased lung volume in ferrets¹⁴. We also reported in human preterm infants without BPD, those treated with CPAP had larger alveolar volumes and lung diffusion versus non-CPAP treated infants when studied after discharge¹⁵. These data suggest a physiologic rationale that CPAP may stimulate lung growth and development.

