Randomization will be done via REDCap by the data management team within strata defined by gestational age at delivery (28 and 6/7 and 29 and 0/7 weeks). If twins are both enrolled they will be allocated to the same treatment arm⁸⁹. A computer generated randomization scheme with stratum using random block sizes of 2 or 4 will be uploaded into REDCap for retrieval. The NICU team will know the treatment allocation but the follow-up research team assessing outcomes will be blinded to the treatment allocation. The electronic medical record will note the infant was in the study, but will not state allocation arm.

i. Assessment of Treatment Adherence

After randomization, the infant will be assessed daily by research staff for the 14 days on the assigned trial arm. As done in the pilot eCPAP study¹⁶, failure criteria for the respective randomization arms will be as follows: Infants randomized to dCPAP (usual care) will be defined as failing if they demonstrate:

- significantly increased work of breathing with a persistent respiratory rate > 75 breaths/ minute,
- o increased apnea and/or bradycardia and/or desaturations > 2 significant episodes in 1 hour in the past 6 hours,
- o oxygen need to maintain oxygen saturations > 86%,
- o a blood gas pH of < 7.2, PaCO2 > 65 mm Hg, or
- o major apnea or bradycardia needing resuscitation 16;86

Subjects who meet the criteria for failing dCPAP will be resumed on their previous level of CPAP. Another attempt to discontinue the subject's CPAP will occur within the next 5 days when they again meet the predefined stability criteria. If the subject does not meet the stability criteria or fails a second attempt at discontinuation, further weaning/management will be by the clinical team. The infant will continue to be studied as intention to treat. In our pilot study¹⁶, only 1 out of 26 subjects failed CPAP discontinuation.

Infants randomized to the eCPAP arm will have the CPAP stopped during the treatment period if there is significant abdominal distension with feeding intolerance or significant nasal breakdown (checked and documented every 3-4 hours as outlined in the OHSU NICU's CCG). The CPAP will be discontinued for up to 5 days and if symptoms resolve, the CPAP will be reapplied. If symptoms reoccur, the CPAP will be removed and further management will be by the clinical team. The infant will continued to be studied as intention to treat. In the pilot CPAP study¹⁶, all 22 patients tolerated eCPAP without adverse events.

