Forced Expiratory Flows (**FEF**₅₀) (**Secondary Outcome**) Measurements in triplicate will be obtained using the raised volume thoracic compression technique that we developed, and previously described^{74,75;83}.

Chloral hydrate sedation: Infant PFTs will be performed at Doernbecher Children's Hospital in sleeping infants following chloral hydrate sedation, as previously described^{68;74;84}. For testing, infants are examined by a physician and continuously monitored by a sedation nurse or health care provider certified in sedation and a respiratory therapist. The parents will be counseled about possible side effects, sign a separate sedation consent, and be given the patient education-discharge instructions. Safety will be monitored as outlined in the DSMB charter.

e. Respiratory Questionnaires

After discharge, a validated respiratory questionnaire will be administered monthly to the infant's primary caregiver ^{83;96} by research personnel blinded to the treatment allocation of eCPAP versus dCPAP in the NICU.. Caregivers are asked about new episodes of wheezing in the previous month, as well as administration of prescribed medications, other illnesses, trips to the emergency room, and hospitalizations. If an infant has wheezing associated with an illness lasting up to seven days, this will be counted as one episode. These questionnaires will be administered in person at the PFT done at approximately 6 months of CGA while the

remainder of the monthly questionnaires will be administered by phone. A small time reimbursement will be available for those patients after each questionnaire is completed.

f. Neurodevelopmental Testing

All preterm infants born at <34 GA are examined in the OHSU Developmental Evaluation Clinic (DEC) if born at OHSU or the PHSW DEC clinic if born at PHSW.at 6 -12 months CGA. This assessment is the standard practice of their care. We will document the Bayley IV neurodevelopmental scores for cognitive, receptive language, expressive language, fine motor, gross motor, and audiology results from these visits^{97;98}. The personnel performing this testing will be blinded to the treatment allocation of eCPAP versus dCPAP in the NICU.

g. Cohort Retention Methods

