Prior to the beginning of the study, research coordinators, respiratory therapists, and study staff will undergo training on all aspects of data collection and procedures at either OHSU in Portland, Oregon or Indiana University in Indianapolis. All personnel must be trained in all applicable study procedures before patient recruitment can begin.

f. Recruitment and Data Collection Period

As in the pilot CPAP study¹⁶, infants will be recruited in the 44 bed NICU at OHSU where [name] is the Director of Neonatal Research. She has been performing infant PFTs here for 15 years as part of research studies^{93;101;102}, so the NICU is familiar with this testing. The number of patients admitted to the OHSU NICU meeting the gestational age inclusion criteria (>24 to \leq 32 weeks gestation) is stable (**Table 4**) and enables the desired sample size to be randomized over 36 months. This will allow trial completion, including patient follow-up to finish within the 5 year grant period.

Table 4. Year	2014	2015	2016	2017	2018	Number needed per year
Infants 24 to ≤32 wks admitted at OHSU/	113	118	128	94	120	36
year						

Recruitment will also occur at PHSW where [name] recruited patients for the VCSIP study. It is a 20 bed NICU that admits approximately 50 infants >24 to ≤ 32 weeks per year.

g. Final Analysis

After a two month period for completion of data entry for the primary outcome of the trial, the data set will be locked and available for analysis. Approximately six months will be required to complete the final report to the eCPAP Steering Committee and to prepare the study's primary paper for publication.

Reference List

- (2) Carlo WA. Gentle ventilation: the new evidence from the SUPPORT, COIN, VON, CURPAP, Colombian Network, and Neocosur Network trials. *Early Hum Dev* 2012;88 Suppl 2:S81-S83.
- (3) [name] C, Schilling D, Peters D, Tillotson C, Spitale P, Wallen L, Segel S, Bowling S, Gravett M, Durand M. Respiratory compliance in preterm infants after a single rescue course of antenatal steroids: A randomized controlled trial. *Am J Obstet Gynecol* 2010; 202: 544.e1-544.e9.

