Specific Aim 1 (Primary Outcome): General linear mixed models (GLMMs) models will be used to compare the primary outcome of alveolar volume (V_A) between the eCPAP and CPAP discontinuation group while adjusting for gestational age at delivery (randomization stratification variable) and other baseline variables that are found to be statistically different between the two groups. Since the lung function measures are highly dependent on infant length and sex, we will further adjust for length and sex in the GLMMs as indicated. In order to adjust for intra-twin correlations, generalized estimating equations (GEEs) with the linear link function will be used to model V_A . The GLMMs can be performed using the GEE estimation approach. Intention to treat analysis will be used for the primary analysis of all aims.

Specific Aim 2 (Secondary Outcomes): Lung diffusion capacity (DLCO) and forced expiratory flows (FEFs) and specifically FEF $_{50}$ will be analyzed with the same general approaches described for the primary outcome of V_A in Specific Aim 1.

FRC measurements in the NICU done pre and post randomization and FEF₂₅₋₇₅, FEF₇₅ done at 6 months of corrected age will be analyzed with the same general approaches as above in Specific Aim 1.

Specific Aim 3 (Exploratory Outcomes): Logistic regression models will be used to compare the incidence of wheeze and the incidence of wheeze and cough between the two groups adjusting for gestational age at delivery (See appendix for standardized respiratory questionnaire administered). Neurodevelopmental scores will be analyzed with the same general approaches described for the primary outcome of V_A in Specific Aim 1.

Intention to treat analysis will be used for the primary analysis of all aims. In addition, all of the aims will also be analyzed with the same general approach using a per protocol analysis and "as treated analysis".

Sample Size and Power Considerations. No studies have compared V_A at 6 months of age in stable infants randomized to eCPAP versus CPAP discontinuation in the NICU. Data from our pilot eCPAP study showed a 12% higher FRC in infants randomized to eCPAP at the end of two week treatment period¹. A study by [name] et al reported a 16% difference in both V_A and D_L in preterm infants according to CPAP treatment in the NICU (Table 1)² and a 12% difference in D_L between infants with BPD versus healthy term infants³. Therefore,

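### Enrolling site is not prespecified in any model after a second NICU and a second Bayley clinic joined the trial; the cost is small for alveolar volume and clearest for the exploratory Bayley scores

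*Protocol*

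**What the plan says.** The protocol amendment history records for version 2.0: "Clarification of measurement of FRC before randomization, addition of PHSW site". Protocol 10.f confirms the second source of infants: "Recruitment will also occur at PHSW where" the VCSIP study had also recruited. Protocol 6.f sends infants for Bayley testing to the OHSU developmental clinic "or the PHSW DEC clinic if born at PHSW".

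Protocol 5.h allocates infants "within strata defined by gestational age at delivery", with two strata and "random block sizes of 2 or 4". Site is not a stratum.

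For V_A, Protocol 7.b1 adjusts for the gestational-age stratum, length, sex and "other baseline variables that are found to be statistically different between the two" groups. The SAP, under Specific Aim 1, keeps the same rule: "other baseline variables that are found to be statistically different between the two groups". DLCO, FEF50 and the neurodevelopmental scores follow the V_A approach. For wheeze, Protocol 7.b3 says: "Logistic regression models will be used to compare the incidence of wheeze and the incidence of wheeze and cough between the two groups", adjusted for gestational age at delivery alone; the SAP agrees. Neither document names site as a stratum, covariate, random effect or subgroup.

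Two statements bear on how much this matters. Protocol 5.e relies on a consistent approach to stopping CPAP at both NICUs. Protocol 6.d places the 6-month lung function tests at OHSU for every randomized infant.

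**The concern.** Site is known before randomization for every infant and may be related to outcome. Because allocation is not stratified by site, the arms can differ by chance in their share of PHSW infants. With site outside the model, any outcome difference between sites stays in the residual variance, and an imbalance that has occurred passes into the estimate.

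The exposure is uneven. For V_A, DLCO and FEFs, site can act only through the infants and their NICU care, because one laboratory tests everyone. For Bayley scores, site also stands for the testing clinic, so a difference between clinics in administration or scoring cannot be separated from site. For wheeze, the models have no route by which site could enter. Bayley and wheeze are exploratory, but Aim 3 is meant to supply pilot data for a multi-center trial, where site differences will need attention.

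**Working it through.** **Inputs from the documents.** Protocol 7.a: V_A mean 642 mL, SD 189, target difference 12%, 34 per group for 80% power, 38 per group after the twin allowance, 50 per group randomized. Protocol 10.f: OHSU admissions of 113, 118, 128, 94 and 120 a year; about 50 a year at PHSW.

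**Assumptions.** The documents give no enrolment split and no site difference. I let enrolment follow admissions: OHSU mean = 573/5 = 114.6, so the PHSW share is 50/164.6 = 0.304, taken as 0.30. I vary the site difference δ over 0.3, 0.5 and 0.8 residual SD. α is taken as two-sided.

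**The plan's own figure.** The target is 0.12 × 642 = 77.0 mL, or 77.0/189 = 0.408 SD (stated as 0.42). Without covariates, n = 2(1.96 + 0.842)²/0.408² gives 95 per group, and 34 per group gives 39% power. The stated 34 is recovered only if the covariates explain R² = 1 − 34 × 0.408²/(2 × 7.85) ≈ 0.64, a value the plan does not state. The implied residual SD is 189 × √0.36 ≈ 113 mL, used below so that the starting point is the plan's 80% power.

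**Precision for V_A without site.** The residual SD is multiplied by √(1 + p(1 − p)δ²), with p = 0.30 and 34 per group. The simulation used 4,000 runs, 68 infants, two gestational-age strata and blocks of 2 or 4.

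| Site difference (residual SD) | SD multiplier | Power by formula, site omitted | Simulated power, site omitted | Simulated power, site included |
|---|---|---|---|---|
| 0.3 | 1.009 | 79.3% | 77.4% | 77.5% |
| 0.5 | 1.026 | 78.0% | 76.9% | 78.6% |
| 0.8 | 1.065 | 74.9% | 73.2% | 78.8% |

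The Monte Carlo standard error of each simulated power is about √(0.78 × 0.22/4000) = 0.7 points. Simulated type I error was about 5% with or without site.

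**Shift from chance imbalance.** The SD of the between-arm difference in PHSW share is √(2 × 0.30 × 0.70/n): 0.111 at n = 34, 0.105 at 38 and 0.092 at 50. The 95% range of the shift in the V_A difference at n = 34 is ±1.96 × 0.111 × δ × 113 mL:

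- δ = 0.3: ±7 mL, 10% of 77 mL
- δ = 0.5: ±12 mL, 16%
- δ = 0.8: ±20 mL, 26%

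For Bayley scores the documents give no SD or target, so the shift can be stated only in residual SD units. At 38 per group, 1.96 × 0.105 × δ gives ±0.06 SD at δ = 0.3 and ±0.10 SD at δ = 0.5.

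**What the significance rule would catch.** A difference in PHSW share reaches p < 0.05 at 1.96 × 0.092 = 18 points with 50 per group, or 1.96 × 0.105 = 21 points with 38. Under randomization that happens about 5% of the time, and only if site is tabulated as a baseline variable, which neither document says. Smaller imbalances are left unadjusted.

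**The case against.** The strongest reply has four parts.

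*One laboratory.* All 6-month V_A, DLCO and FEF tests are done at OHSU by blinded staff, with blinded off-site review. This stands, and it removes measurement differences between sites for the primary outcome. It does not cover the Bayley clinics.

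*Common care.* One neonatology division serves both NICUs, entry and stability criteria are the same, and the protocol claims a consistent weaning approach. This makes a large site effect on V_A less plausible. It says nothing about the families or infants each hospital admits, but the documents do not show that these differ either. Nor do they say that different examiners staff the two clinics; they do say that testers are blinded.

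*The covariate rule.* A reader might infer that site can never enter a model, or that a 20-point imbalance would go uncorrected and move the result by 15 to 25% of the target. Neither is supported. At 50 per arm, 40% against 20% PHSW gives z = 0.20/0.092 = 2.18, p ≈ 0.03, so the plan's own rule would admit site to the V_A, DLCO, FEF and Bayley models if site were tabulated. The 15 to 25% also assumes a site difference of 0.3 to 0.5 of the total SD, that is 57 to 95 mL, or 74 to 123% of the treatment effect sought. Nothing in the documents supports so large a difference. What survives is that the rule depends on the data, misses moderate imbalances and does not reach wheeze.

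*Chance is already in the standard error.* True: over repeated randomizations the unadjusted comparison is valid, so the issue is efficiency and balance in the trial actually run.

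The PHSW share is also uncertain. Protocol 10.a still describes a single clinical center, and the SAP's screened population covers only infants delivered at OHSU.

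**Conclusion.** The omission is real but modest. Site is neither a stratum nor a prespecified covariate; its only route into the V_A, DLCO, FEF and Bayley models is a significance rule that would trigger about 5% of the time, and it has no route into the wheeze models. A reader might infer bias or an inflated false-positive rate. The documents and the calculation support neither.

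For V_A, with a 30% PHSW share and site differences of 0.3 to 0.5 residual SD, both assumed, the cost is about 0 to 2 power points and a chance shift within about ±7 to ±12 mL of a 77 mL target. Only at 0.8 residual SD does the loss reach about 5 points. The case is weakest for V_A, DLCO and FEFs and strongest for the exploratory Bayley scores. It does not depend on whether the planned 34 per group can be reproduced.

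**What to change.** Before unblinding, add one sentence to the SAP: enrolling site (OHSU or PHSW) enters every Aim 1 to 3 model as a fixed covariate alongside the gestational-age stratum, whether or not it differs between arms. If the change is made only in part, the Bayley and wheeze models come first. Randomization and data collection need not change.

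In the same edit, reconcile the single-center statement in Protocol 10.a and the OHSU-only screened population in the SAP with the two-site text, and report enrolment by site and arm.

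The cost is one degree of freedom per model, and the wheeze odds ratio becomes conditional on site as well as gestational age. If PHSW enrols few infants, the gain is small.
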